1 OBJECTIVES

The *premise* of this study is that flavors or synthetic nicotine might be related to the phenomenon of ‘indirect’ toxicity. That is, regardless of whether the compounds show evidence of toxicity in a biological sense, they may nonetheless increase harm by other means, such as altering vaping topography (puffing) patterns, increasing appeal, decreasing risk perceptions, or masking harshness or irritation that might lead users to discontinue use.

1.1 Primary Objectives

- Examine the influence of tobacco flavoring composition on vaping topography
- Examine the influence of synthetic vs. tobacco derived nicotine on vaping topography

1.2 Secondary Objectives

- Examine differences in sensory and subjective effects by tobacco flavoring composition
- Examine differences in sensory and subjective effects by synthetic vs tobacco derived nicotine

1.3 Exploratory Objective

- To generate a cell line/tissue from optionally provided oral cell samples to demonstrate the feasibility of cell line/tissue generation and later, expose oral cells to the study products or product constituents to examine the cellular-level effects of the study products and their components.

2 BACKGROUND

To appreciate the potential role of flavor perception in the use of tobacco products, it is instructive to look at the broader literature on subjective effects and responses to the sensory properties of tobacco products. In general, tobacco products were designed in part with sensory factors in mind, in order to maximize appeal to different market segments (1-4). Rees et al. (5) suggest a framework of consumer response that groups responses into two broad classes: response to the product, including drug effects and sensory perceptions; and perceptions of messaging around that product, including advertising and packaging. Much of this literature is focused on cigarettes given their greater prevalence but is nonetheless instructive for examining other tobacco products. Sensory blockade reduces urge to smoke, providing indirect evidence for the importance of sensory factors in maintaining behavior (6, 7), and a body of work has attempted to dissociate the sensory and drug components of smoking (8-14). Flavors may also influence expectancies around tobacco products. Expectancies of positive sensory effects of smoking (e.g., look, feel, and taste) are predictive of smoking behavior and willingness to try different types of cigarettes (15-21).

Understanding how nicotine vaping products (NVP) are used by consumers in the real world is an important component of properly assessing their individual and population level health impacts. While not as extensively studied as cigarette smoking topography, vaping topography has been shown to vary as a function of product design (Hiler et al., 2020 (22); Spindle et al., 2018 (23); Kimber et al., 2021(24)) and to be related to aldehyde emissions (Talih et al., 2015 (25); Son et al., 2020 (26)). From a regulatory perspective, understanding patterns of puffing (vaping topography) is crucial to informing standardized vaping regimens, which can be used to compare products across brands and classes. A total of 32 studies published between 2013 and April 2021

Roswell Park Protocol No.: I-3234822

have directly measured NVP puff topography, and reported mean values for key topography parameters (puff duration, volume, flow rate, interval). CORESTA protocols (3s, 55mL, 18.33 mL/s, 30 s interval) commonly underestimated puff volume and flow rate, for example, for NVP-experienced users (112.15 ± 18.9 mL, 37.94 ± 7.67 mL/s) and open NVPs (112.98 ± 20.97 mL, 40.65 ± 8.57 mL/s). Underestimation of puffing parameters such as puff volume may lead to underestimation of NVP nicotine and toxicant yields, causing miscommunication of information to consumers and regulators. Additional research is necessary to determine whether flavoring chemicals or type of nicotine used in the product are further confounds for measuring vaping topography.

3 INCLUSION AND EXCLUSION CRITERIA

3.1 Inclusion Criteria

To be included in this study, subjects must meet the following criteria:

1. Age ≥ 21 and ≤ 55 years.
2. Current daily vapers of products containing nicotine.
3. No daily concurrent use of other tobacco products.
4. Self-reported general good health.
5. Women of childbearing potential must be willing to provide a urine sample and test negative prior to receiving any study-related products/procedures.
6. Ability to speak, read, and write in English.
7. Participant must understand the investigational nature of this study and sign an Independent Ethics Committee/Institutional Review Board approved written informed consent form prior to receiving any study related procedure.

3.2 Exclusion Criteria

Subjects will be excluded from this study for the following:

1. Allergies - active untreated seasonal allergies that would interfere with smell or taste procedures.
2. Self-reported taste or smell deficits.
3. Pregnant or nursing female participants.
4. Medications known to interfere with taste/smell (i.e., certain nasal sprays, nasal antihistamines, decongestants, antibiotics, medications containing zinc).
5. Unwilling to use open system vaping device in laboratory setting.
6. Positive diagnosis of COVID-19 within 10 days prior to start of study intervention.
7. Unwilling or unable to follow protocol requirements.
8. Any condition which in the Investigator's opinion deems the participant an unsuitable candidate to receive the study intervention.

Roswell Park Protocol No.: I-3234822

3.3 Special Populations

The following special population groups are EXCLUDED from participation:

- Cognitively impaired adults/adults with impaired decision-making capacity
- Individuals who are not yet adults (infants, children, teenagers)
- Pregnant women
- Prisoners
- Adults aged 18-20 unable to legally purchase tobacco in New York State

3.4 Inclusion of Women and Minorities

Both men and women and members of all races and ethnic groups are eligible for this study.

4 LOCAL AND STUDY-WIDE NUMBER OF SUBJECTS

A maximum of 72 evaluable participants from the general population in the greater Buffalo area and Rochester will be enrolled.

5 LOCAL AND STUDY-WIDE RECRUITMENT METHODS

Adult participants are recruited by offered continuation of another study and local advertising. We will recruit via community events, contacts, ad postings in local daily, weekly, and college newspapers, websites such as Craigslist, any social media networks (i.e.: Facebook, Instagram, Twitter, Snapchat, etc.), local tobacco control networks (methods we have previously used to recruit successfully), television, and radio (see **Appendix A** for example).

Participants will be recruited from the general population, not from within the RPCI or URMC patient populations.

Participants will be compensated via 1) an Amazon Gift Card Code sent to their provided email (all sites), 2) direct deposit (URMC only), or 3) a physical Visa Gift Card (URMC only). A gift card code/deposit/card reload notification will be sent within 24-48 hours of the session completion. Funds (via Amazon Gift Card Code) are immediately available when added to their Amazon account and participants can check their balance as desired. This system will allow frequent, immediately available payments. Compensation will be given on an escalating schedule upon successful completion of each session. A \$50 bonus will be given upon successful completion of all seven sessions. The escalating compensation schedule will be as follows:

- Session 1: \$25
- Sessions 2 - 5: \$30
- Sessions 6 & 7: \$50
- Completion Bonus: \$50

6 MULTI-SITE RESEARCH

University of Rochester Medical Center (URMC) will be an additional study site. The site PI is [name]. A reliance agreement will be entered wherein Roswell Park is the IRB of record. It is the responsibility of the Principal Investigator to ensure that:

Roswell Park Protocol No.: I-3234822

- All sites have the most current version of the protocol and consent document.
- All required approvals (initial, continuing review and modifications) have been obtained at each site (including approval by the site's IRB of record).
- All modifications have been communicated to sites, and approved (including approval by the site's IRB of record) before the modification is implemented.
- All engaged participating sites will safeguard data, including secure transmission of data, as required by local information security policies.
- All local site investigators will conduct the study in accordance with applicable federal regulations and local laws.
- All non-compliance with the study protocol or applicable requirements will be reported in accordance with local policy.

7 STUDY TIMELINES

Participants will complete up to 7 laboratory visits (approximately 1½ hour/visit) over about a 3 month period. Each visit will be scheduled a minimum of 24 hours and a maximum of 1 week apart. The time between visits may be extended up to 14 days (2 weeks) due to participant illness (e.g., COVID, influenza).

The total duration of the recruitment is 18 months with an approximate study completion date of 8-31-2024.

8 STUDY ENDPOINTS

8.1 Primary Endpoints

The primary endpoints are measures of vaping topography [(per-puff volume, inter-puff interval, peak flow rate, puff count, total volume (sum of volumes across all puffs)], which are treated as quantitative outcomes and will be summarized by:

- Condition (flavor or nicotine composition) and,
- Bout (directed or ad-lib) using the appropriate descriptive statistics.

8.2 Secondary Endpoints

The same type of modeling employed for the primary endpoints will be used to evaluate the effect of flavoring and nicotine formulation on sensory and subjective measures, such as:

- Sensory measures – irritation, harshness
- Drug effects – liking.

8.3 Exploratory Endpoint

- Oral cell samples will be used for cell line/tissue generation to examine the cellular-level effects of the study products and their components.

Roswell Park Protocol No.: I-3234822

9 DESIGN

This is an open-label, factorial multi-center study of e-liquid composition and effects on vaping topography.

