11.3 Session Procedures

Once a participant is identified as eligible, a visit date and time will be scheduled.

Participants will complete all experimental conditions, and are to abstain from vaping for a minimum of 30 minutes prior to the study session.

Roswell Park Protocol No.: I-3234822

The order of completion of Sessions 2-5 and 6-7 will be determined using Latin Square and A/B designs, respectively. Order of ad lib and directed bouts within a session will be determined by A/B designs.

Each laboratory session is expected to take approximately 90 minutes.

Directed vs. ad lib bouts. In the directed bout, participants are instructed to take a 4 second puff on the device every 60 seconds until a total of 8 puffs is reached. In the ad lib bout, participants are free to puff as they like for a defined 15 minute period.

Priming / Habituation Puff: At the beginning of each session, participants will take 1 priming puff and 1 habituation puff at a setting of 10 watts. If 10 watts is too harsh for the participant, wattage may be reduced by 2 until comfort level is obtained. Final wattage will be recorded and used throughout the session.

Session 1: Vaping topography using own-brand liquid

In this condition, we will use an A/B design to compare directed vs ad lib vaping of the participant's preferred product. After each bout, participants will complete a battery of sensory outcome measures. All questionnaires will be administered by the experimenter. Vape assembly and puffing regimen will also be directed by the experimenter. The device used will be a SmokTech® NORD2 or equivalent device. This session will be approximately 90 minutes long.

Sessions 2-5: Relationship of tobacco flavor formulation to vaping topography and sensory evaluation.

In this condition, we will use a 4 (flavor) x 2 (ad lib vs directed) within-subjects design. All liquids will have a 60/40 carrier concentration and 5% nicotine. Three commercial tobacco flavor variants versus one unflavored liquid (EC Blend) will be tested.

Over 4 laboratory sessions (sequence determined by Latin square), participants will complete ad lib and directed bouts (sequence determined by A/B design) using each flavor. After each vape, participants will complete a battery of sensory outcome measures. All questionnaires will be administered by the experimenter.

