Vape assembly and puffing regimen will also be directed by the experimenter. The device used will be a SmokTech® NORD2 or equivalent device. These sessions will be approximately 90 minutes long.

Sessions 6-7: Relationship of nicotine formulation to vaping topography and sensory evaluation.

In this condition, we will use a 2 (nicotine form) x 2 (ad lib vs directed) within-subjects design. All liquids will have a 60/40 carrier concentration and 5% nicotine. The primary comparison is between 5% synthetic nicotine and 5% tobacco-derived nicotine.

Over 2 laboratory sessions (sequence determined by A/B design), participants will complete ad lib and directed bouts (sequence determined by A/B design) using each liquid form. After each vape, participants will complete a battery of sensory outcome measures. All questionnaires will be administered by the experimenter.

Vape assembly and puffing regimen will also be directed by the experimenter. The device used will be a SmokTech® NORD2 or equivalent device. These sessions will be approximately 90 minutes long.

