19 STATISTICAL PLAN

This is an open-label, factorial-design, multi-center study of e-liquid composition and effects on vaping topography.

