32 DRUGS OR DEVICES

During each visit, participants will be asked to use E-liquids (unflavored, tobacco flavor). The primary psychoactive ingredient in all products is nicotine. All products are currently available for commercial purchase and will be purchased by the research team either online or at local stores (e.g., tobacco/vape shops, convenience store). These nicotine-containing products will be stored in a cool, dark location in laboratories or offices that are locked and only accessible to those with a key. When participants are randomized to a condition, the laboratory staff session will retrieve only the product needed for the individual session and will bring it directly to the participant in the lab.

Under no circumstances will the Investigator allow the study product to be used in a manner other than as directed by this protocol.

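### The plan is open-label with no step to withhold liquid identity, so label expectancy may be confounded with composition, most of all for synthetic versus tobacco-derived nicotine

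*Combined protocol and SAP*

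**What the plan says.** Section 9 gives the design as "This is an open-label, factorial multi-center study of e-liquid composition and effects on vaping topography", and Section 19 opens the statistical plan in the same way: "This is an open-label, factorial-design, multi-center study of e-liquid composition and effects on vaping topography". Neither gives a reason for leaving the liquids open. No section describes masking, a rule against naming the liquid, or a question about what participants believe they used.

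The comparisons are of composition. For Sessions 2-5, Section 11.3 says: "Three commercial tobacco flavor variants versus one unflavored liquid (EC Blend) will be tested". For Sessions 6-7 it says: "The primary comparison is between 5% synthetic nicotine and 5% tobacco-derived nicotine". All these liquids share a 60/40 carrier and 5% nicotine.

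On handling, Section 11.3 says: "Vape assembly and puffing regimen will also be directed by the experimenter". Section 32 adds that "the laboratory staff session will retrieve only the product needed for the individual session and will bring it directly to the participant in the lab". On ratings, Section 11.3 says: "All questionnaires will be administered by the experimenter". The Product Evaluation Scale in Appendix C has a blank Product Code field, but no text says what the code is for.

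On expectancy, Section 2 says: "Flavors may also influence expectancies around tobacco products". It then notes that expectancies of positive sensory effects predict smoking behavior and willingness to try different cigarettes.

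**The concern.** The primary endpoints (Section 8.1) include ad lib topography, where the participant decides how to puff for 15 minutes. The secondary endpoints (Section 8.2) are self-ratings of irritation, harshness and liking. Both can respond to what a person believes is in the device. If that belief comes from a name, a difference between liquids could reflect the name, the composition or both. A name effect in the opposite direction could also hide a real composition effect.

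This bears most on the nicotine comparison, which is one of the two primary objectives. With carrier and strength held equal, the word synthetic could be one of the main cues that tell the two liquids apart.

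**Working it through.** **1. Can the design or the model separate label from composition?** For a participant's paired difference D between two liquids in one type of bout, E(D) = c + l. Here c is the composition effect and l is the effect of knowing the name. Randomized order (Sections 11.3 and 19.2) balances period effects, but the name goes with the liquid in every order, so l does not average out. The Section 19.4 models contain liquid, bout, their interaction, and random subject and site effects. A label term could not be added, because it would coincide exactly with the liquid term. If names are known, only c + l can be estimated.

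**2. Which outcomes are exposed?**

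| Comparison or outcome | Exposure | Reason |
|---|---|---|
| Synthetic vs tobacco-derived nicotine, ad lib puffing and ratings | Strongest | Same carrier and strength; the name may be a main cue |
| Among the three tobacco flavors, ad lib puffing and ratings | Next | Taste may tell them apart in part |
| Flavored vs unflavored | Weaker | Taste may reveal the liquid; Section 3.2 excludes people with taste or smell deficits |
| Directed-bout puff count and inter-puff interval | Weaker | Section 10 prescribes 8 puffs of 4 seconds, one every 60 seconds |
| Own brand (Session 1) | Cannot be masked | The participant uses a preferred product |

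Puff volume and peak flow rate are not prescribed in the directed bout, so the protection there is partial.

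**3. Reproduce the plan's figures (Section 19.1).** The inputs are 72 participants, 5-10% attrition per session, a two-sided paired t-test and alpha 0.05. Expected completers of Session 7 are 72 × 0.95^6 = 52.9 and 72 × 0.90^6 = 38.3, which match the tabled 53 and 38. Power comes from the noncentral t with n − 1 degrees of freedom and noncentrality d√n, where d is in SDs of the paired difference.

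- n=38, d=0.47: noncentrality 0.47 × √38 = 2.90, power 80.5% (exact detectable difference 0.467)
- n=53, d=0.39: noncentrality 0.39 × √53 = 2.84, power 79.6% (exact detectable difference 0.392)

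The stated 0.47 and 0.39 SD reproduce.

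**4. Illustration for Sessions 6-7.** The label shift is an assumption, shown as a range. Set c = 0 and l = 0.1, 0.2 or 0.3 SD, and use noncentrality l√n in the same test.

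| Assumed label shift (SD) | Rejection rate, n=38 | Rejection rate, n=53 |
|---|---|---|
| 0.1 | 9.2% | 11.0% |
| 0.2 | 22.5% | 29.8% |
| 0.3 | 43.7% | 57.3% |

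If the shift opposes a real effect of the size the plan is powered for, use noncentrality (d − l)√n.

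| Opposing shift (SD) | Power, n=38, d=0.47 | Power, n=53, d=0.39 |
|---|---|---|
| 0.1 | 60.3% | 54.5% |
| 0.2 | 36.8% | 27.4% |
| 0.3 | 17.5% | 9.9% |

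These sample sizes are Session 7 counts and so apply to the nicotine comparison. The flavor sessions end at Session 5, where the table gives 47 to 59 completers.

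**The case against.** The strongest reply is that the harmful fact is not written down. No section says that participants are told or shown the liquid's name. That is inferred from the word open-label, and the Product Code field would fit liquids that are already coded. This stands: a reader might infer that disclosure is established, and it is not. It does not close the point. If codes do hide identity, Sections 9 and 19 describe the study wrongly; if they do not, the confounding is real. The text needs changing either way.

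A reader might also take the background to say that labels change responses. It says only that flavors may influence expectancies and that expectancies predict behavior. It does not discuss product names or the word synthetic. It makes label expectancy plausible on the protocol's own terms and proves nothing about its size.

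A third reply is that the eTop device records puffing objectively and that the self-ratings are secondary. The measurement is objective, but ad lib behavior can still respond to belief. The reply does carry weight for directed-bout puff count and timing.

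Two further limits stand. Taste may defeat masking of flavored versus unflavored liquid, so it would be wrong to treat Sessions 2-7 as equally affected. Masking participants also leaves possible cueing by the experimenter, who directs assembly and administers the questionnaires.

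**Conclusion.** The concern holds, conditionally. If participants know which liquid they are using, label and composition cannot be separated for ad lib puffing and the self-ratings, and no analysis in Section 19 repairs this. It is most serious for synthetic versus tobacco-derived nicotine, then for contrasts among the three tobacco flavors.

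The rejection rates (9% to 44% at n=38, 11% to 57% at n=53) show only that a label shift smaller than the 0.39 to 0.47 SD the study is sized to detect would matter. They assume a net shift in one direction and use the plan's paired t-test in place of its mixed model. A reader might take them as the expected error rates of this trial. The documents do not support that, because they give neither the size nor the direction of any label effect.

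**What to change.** Change Sections 9 and 19 to say that participants are masked to liquid identity in Sessions 6-7 and, as far as taste allows, in Sessions 2-5. To carry this out:

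- Put the study liquids in coded containers and record the code in the existing Product Code field.
- Load the device out of the participant's view. Staff already fetch the single product for each session, although the text does not say who fills the device.
- Have the consent form list the set of liquids, and disclose the order only after Session 7.
- Keep Session 1 open, and report own-brand contrasts from the Sessions 1-5 model as unmasked.

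If codes already hide identity, correct the open-label wording and describe the procedure instead.

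The cost is protocol and consent wording plus a small coding and loading step at two sites. It is not free: a reader might assume that no extra procedure is needed because the experimenter directs assembly, but coding and out-of-view loading are new steps. Masking of flavors will be imperfect, and cueing by the experimenter remains possible. No sample-size figure changes.

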10 STUDY INTERVENTION

Participants will vape twice per session – once directed and once ad lib. In the directed bout, participants are instructed to take a 4 second puff on the device every 60 seconds until a total of 8 puffs are completed. In the ad lib bout, participants are free to puff as they like for a defined 15 minute period.

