19.4 Primary Analysis

The primary objective is to evaluate the influence of:

Roswell Park Protocol No.: I-3234822

- a. tobacco flavoring composition on vaping topography
- b. synthetic vs. tobacco derived nicotine on vaping topography

The primary endpoints are measures of vaping topography, which are treated as quantitative outcomes and will be summarized by condition (flavor or nicotine composition) and bout (directed or ad-lib) using the appropriate descriptive statistics.

Using data from sessions 1-5, each endpoint will be modeled as a function of flavoring (own, none, and 3 commercial flavors), bout (directed or ad-lib), their two-way interaction, and random subject and site effects using a linear mixed model. Tests about the appropriate contrasts of model estimates will be used to compare:

- i) mean differences between flavors within a type of bout,
- ii) mean differences between bouts within a flavor,
- iii) effects of bout (ad lib – directed) between flavors,
- iv) effect of flavor between bouts.

Using data from sessions 6 & 7, each endpoint will be modeled as a function of nicotine composition (synthetic vs. tobacco derived), bout (directed or ad-lib), their two-way interaction, and random subject and site effects using a linear mixed model. Tests about the appropriate contrasts of model estimates will be used to compare:

- i) mean differences between composition within a type of bout,
- ii) mean differences between bouts within a composition,
- iii) effects of bout (ad lib – directed) between compositions,
- iv) effect of composition between bouts.

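### Puff count and inter-puff interval are set by instruction in directed bouts, yet Section 19.4 runs primary tests on them there, between bouts and in the interaction

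*Combined protocol and SAP*

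**What the plan says.** Section 10, repeated in Section 11.3, defines two bouts per session. For the directed one, each person is "instructed to take a 4 second puff on the device every 60 seconds until a total of 8 puffs are completed"; the other, ad lib, allows free puffing for 15 minutes. Section 10.2 expects almost no noncompliance with product use. Section 17.1 lets a participant stop using the product during a session and remain in the study.

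Section 8.1 lists the primary endpoints as "per-puff volume, inter-puff interval, peak flow rate, puff count, total volume (sum of volumes across all puffs", summarised by condition and by bout.

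Section 19.4 models each endpoint on liquid, bout and their interaction, with "random subject and site effects using a linear mixed model". One model covers flavoring (sessions 1-5) and one covers nicotine source (sessions 6-7). The flavor contrasts include "mean differences between flavors within a type of bout", "mean differences between bouts within a flavor" and "effect of flavor between bouts"; the nicotine model has the matching set. No section limits puff count or inter-puff interval to ad lib bouts, treats their directed values as a compliance check, or states a residual variance structure.

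**The concern.** The primary objective is whether flavoring or nicotine source influences how people puff. In a directed bout the number and spacing of puffs are prescribed. A directed contrast between liquids on either measure therefore says mainly how far people departed from the instruction. A null result there could be misread as evidence that the liquid has no effect on puffing. A bout contrast sets free puffing against a value largely known in advance.

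The second consequence concerns the contrast that does carry the evidence. If directed and ad lib data share one residual variance, the ad lib standard error is estimated partly from data that the instruction makes less variable. The estimate stays unbiased, but the test may not hold its 5% level. Two of the five primary endpoints are affected.

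**Working it through.** **The plan's own figure.** Section 19.1 gives detectable paired differences of 0.47 SD (n = 38) and 0.39 SD (n = 53) at 80% power and two-sided 5%. The exact paired t-test gives 0.467 and 0.392, and 72 × 0.90^6 = 38.3 and 72 × 0.95^6 = 52.9. These figures reproduce and are not at fault. They cannot describe a contrast whose values are nearly fixed by instruction.

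**What the regimen fixes.** With full adherence the directed count is 8 for every liquid. Puffs start 60 s apart (a gap of 60 − 4 = 56 s), and the bout spans 7 × 60 + 4 = 424 s, about 7 minutes against 15 for ad lib. The expected directed difference between liquids is zero, and the bout contrast for puff count becomes the ad lib mean minus 8.

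**How much early stopping adds.** Assume a fraction p of directed bouts stop, uniformly, at 1 to 7 puffs. The variance is 20p − (4p)². At p = 0.10 this is 1.84, an SD of 1.36 puffs, and the mean falls by only 0.4 puffs. As a share d of ad lib variance:
- assumed ad lib SD of 10 puffs: 1.84/100 = 1.8%
- SD of 5: 1.84/25 = 7.4%
- SD of 3: 1.84/9 = 20%

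**Interaction.** Scale ad lib variance to 1, with within-person correlation ICC. If directed departures are independent of the person, the interaction contrast correlates with the ad lib contrast at √[(1 − ICC)/(1 − ICC + d)].

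| d | ICC 0.8 | ICC 0.3 |
|---|---|---|
| 1.8% | 0.96 | 0.99 |
| 7.4% | 0.85 | 0.95 |
| 25% | 0.67 | 0.86 |
| 50% | 0.53 | 0.76 |

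**Size of the ad lib test under one residual variance.** Take complete data, K liquids (5 in the flavor model including own brand, 2 for nicotine) and 2K cells per person with covariance matrix Σ. The fitted residual variance has expectation [tr Σ − (sum of all elements of Σ)/(2K)]/(2K − 1); the true value for an ad lib contrast is 1 − ICC. Call their ratio R. With no person component in the directed values:

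- flavor: R = 0.5 + 0.278·ICC/(1 − ICC) + 0.5·d/(1 − ICC)
- nicotine: the same with 0.333 in place of 0.278
- size = 2[1 − Φ(1.96√R)]

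For flavor at ICC 0.3 and d = 0, R = 0.5 + 0.278 × 0.429 = 0.619, so size = 2[1 − Φ(1.54)] = 12.3%. R reaches 1 at an ICC of about 0.64 (flavor) and 0.60 (nicotine); the test is liberal below that and conservative above it.

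If directed departures are instead person-specific, with a directed person effect proportional to the ad lib one and the same ICC, the sum of elements becomes K(1 − ICC)(1 + d) + K²·ICC·(1 + √d)². For flavor at d = 0.25 and ICC 0.3: trace 6.25, sum 4.375 + 16.875 = 21.25, expectation (6.25 − 2.125)/9 = 0.458, R = 0.458/0.7 = 0.655, size 11.3%.

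| Directed variance | Person component | Flavor, ICC 0.3 / 0.5 / 0.8 | Nicotine, ICC 0.3 / 0.5 / 0.8 |
|---|---|---|---|
| 0 | – | 12.3 / 8.4 / 1.3% | 11.6 / 7.4 / 0.8% |
| 25% of ad lib | none | 8.0 / 4.7 / 0.3% | 7.6 / 4.1 / 0.2% |
| 25% of ad lib | proportional | 11.3 / 10.2 / 6.3% | 11.1 / 9.9 / 5.5% |

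**Simulation.** A random-intercept REML fit with 72 subjects, 7.5% attrition per session, 10% early stops and an ad lib SD of 10 puffs (10,000 runs per setting) gave 12.2%, 8.6%, 1.6% for flavor and 12.0%, 8.0%, 1.3% for nicotine at the same three ICCs. Bias was negligible (at most 0.0023 SD). A fit to ad lib data only, with a t reference, had size 4.8% to 5.3% throughout. The site effect was left out because these contrasts are within person.

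**The case against.** Much can be said for the plan. The contrast that answers the objective, between liquids within ad lib bouts, is already listed and unbiased. The regimen is an instruction and not a device lock. Early stopping is allowed, and Section 1 names "masking harshness or irritation that might lead users to discontinue use" as a route to harm, so fewer directed puffs with a harsher liquid could be a real liquid effect. The bout comparison is deliberate: for Session 1 the protocol states that "we will use an A/B design to compare directed vs ad lib vaping" of the participant's own product. Section 19.4 speaks only of appropriate contrasts, which leaves the analyst some discretion, and a single residual variance is an assumption of this review. In null simulations with one residual variance the extra tests were not liberal: the directed contrast rejected in 0.0% of runs and the interaction in 0.2% to 4.1%.

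Most of this stands and limits the point. It does not remove it. The listed contrasts apply to each endpoint, and discretion exercised after the data are seen is what a prespecified plan should avoid. Bout-specific variances would repair calibration but would not make a directed count informative about free puffing. A real tolerability effect shows more clearly as early stops by liquid than as a mean count that moves by 0.4 puffs when one bout in ten stops early.

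A reader might infer three stronger things that the documents do not support:
- That the directed values are constants and carry no information. Early stops and timing drift are possible.
- That the interaction always duplicates the ad lib contrast. This holds only when directed variance is small.
- That the ad lib p-values will be too small. The documents give no ICC, variance or residual structure, and the error can run either way.

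**Conclusion.** The point holds and should be settled before analysis. As written, two of five primary endpoints receive primary tests that mainly reflect the instruction. This part rests on the text alone. The near-repetition of the ad lib contrast by the interaction is limited to directed variance under about 7% of ad lib variance, with departures independent of the person (correlation 0.85 to 0.99 at ICC 0.8 to 0.3).

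The effect on the ad lib p-value is conditional on one residual variance being fitted. With near-constant directed values the size runs from 12.3% down to 1.3% (flavor) and from 11.6% down to 0.8% (nicotine) over ICC 0.3 to 0.8. With more directed variance, size and direction also depend on whether departures are person-specific, so the tabulated values are illustrations and not bounds. For inter-puff interval the documents give no timing error, so d is open. The ICC, the variances, the early-stop rate and the residual structure are all assumptions. The data remain usable for the objective.

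**What to change.** In Section 19.4, state that for puff count and inter-puff interval the primary flavor and nicotine tests use ad lib data only, with a t reference (Kenward-Roger or Satterthwaite degrees of freedom). Report directed values for these two endpoints, including early stops by liquid, as an adherence and tolerability summary. Report the ad lib minus directed difference descriptively against the instructed regimen.

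For total volume, whose directed value is partly set by the 8 instructed puffs, allow bout-specific residual variance. Interpret its bout contrast in light of the instructed count and the unequal puffing time (about 7 against 15 minutes). Per-puff volume and peak flow rate keep their planned contrasts.

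The cost is SAP wording and a subset fit. The downside is that the directed, bout and interaction contrasts for the two endpoints move from primary tests to description. The puffing regimen, data collection and sample size do not change.
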